3.1 Investigational product/treatment

Treatment will be provided according to the 'TREATMENT GUIDELINES for Esketamine Nasal Spray for the use of treating Physicians' as provided by the manufacturer.

In brief, treatment will be provided initially twice per week during the Induction Phase, followed by a Continuation (maintenance) Phase, where in week 5-8 treatment will be provided once weekly and from week 9 onwards dosing can be tried to be reduced to once every two weeks (Figure 1). Usual initial dosages are 56mg/session, which may be increased to 84mg/session. Especially in elderly the initial starting dose will be lower (28mg/session), and if responsive, patients may stay on that dosage. Dosing frequency will be individualized to the lowest frequency to maintain remission/response. At the end of Induction Phase, evidence of therapeutic benefit (based on the clinician's evaluation of symptomatic change and/or improvement in functioning or quality of life) will be evaluated to determine need for continued treatment in the Continuation (maintenance) Phase. After depressive symptoms improve, treatment is recommended for at least 6 months.

Each treatment session consists of administration of esketamine nasal spray and post-administration observation under the supervision of a healthcare professional. Patients will administer the nasal spray themselves. Because of possible nausea and vomiting after administration of esketamine nasal spray, patients should not eat for at least 2 hours before administration and not to drink liquids at least 30 minutes prior to administration. Patients who require a nasal corticosteroid or nasal decongestant on a dosing day should be advised not to administer these medications within 1 hour before administration of esketamine nasal spray.

All patients remain at the clinical site until safety procedures have been completed (monitoring of blood pressure and dissociative symptoms) and the patient is ready for discharge. Readiness to leave is assessed based on clinical judgement of dissociative symptoms measured 40 minutes after the last dose administered or as soon as possible after the patient wakes up. Patients must not drive a car or work with machines for 24 hours after esketamine dosing, therefore patients need to have transportation home after the procedure.

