6.1.2 Secondary study parameters/endpoints

Secondary endpoints are:

- The change (relative to baseline) in clinician-rated MADRS score (Montgomery 1979) over time measured in 4 weeks intervals after week 8.
- The change (relative to baseline) in self-rated IDS-SR score (Rush 1996; Trivedi 2004) at 4 weeks and over time measured in 4 week intervals thereafter.
- Quality of Life measurement (EQ-5D-5L; Janssen 2013) at 4 weeks and over time measured in 4 week intervals thereafter (relative to baseline)
- Level of functioning at 4 weeks (WHODAS-2.0; Forero 2018) and over time measured in 4 week intervals thereafter (relative to baseline)
- Cost-effectiveness (modified TiC-P) at 4 and 8 weeks and 3 monthly intervals thereafter (relative to baseline)
- The change in mood (before-after) esketamine intranasal spray per session as measured by a visual analogue scale before administration and after completion of the session (before leaving).
- Occurrence of adverse effects including dissociative symptoms at T=40 min after administration (or as close as possible) and at the end of the session as measured with the KSET (Short 2020) per session
- Discontinuation rates: due to adverse effects of the treatment or other reasons.
- Changes in blood-pressure during esketamine intranasal sessions (baseline, 10, 40, 90 minutes)
- Follow-up 3 months after discontinuation of intranasal esketamine treatment.

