6.3 Study procedures

All procedures are part of routine clinical practice. No invasive or additional measurements will be done.

Initial assessment for eligibility for esketamine intranasal treatment consists of:

- Assessment of in- and exclusion criteria including determination of DSM-5 diagnosis by either clinical or semi-structured clinical interview.
- Level of treatment resistance (DM-TRD)
- Drug and alcohol screening (if appropriate)
- Pregnancy test (if appropriate)
- Routine ECG and laboratory assessment
- Assessment of baseline MADRS and IDS-SR score

- Internet-based delivery of PIT test via GDPR certified online testing platform Gorilla

After inclusion, patients will continue the antidepressant they are currently using. This treatment might be optimized according to dosing or TDM. Patients start treatment in accordance with the schedule provided by the manufacturer and described under 4.1 (Figure 1).

Every session:

- VAS-ratings of mood will be asked at every session before-after esketamine administration
- Adverse effects including dissociation at 40 minutes after the last dose of esketamine, or – in case of more pronounced dissociation- as close as possible and at the end of the session (KSET)

During the Induction Phase weekly assessments of effectiveness will be done. In the Continuation (maintenance) Phase this will be continued every second week at frequencies of administration $\geq 1/\text{week}$, while if the frequency is $\leq 1/2 \text{ weeks}$, assessments will be done monthly for the first 2 months, followed by every two months thereafter:

- Repeated assessments of MADRS and IDS-SR scores.

Formal evaluations of the treatment will be performed at regular intervals according to clinical judgement. The first evaluation of effectiveness will be after 4 weeks of twice weekly administration. This will also be the second and last time that the subject is asked to do the online PIT test.

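### The long-term endpoints are set on a 4-weekly grid, but Section 6.3 assesses patients on reduced dosing only every two months after an initial period, so who is observed depends on response; three change-from-baseline questionnaires are also absent from Section 6.3.

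*Protocol*

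**What the plan says.** **Endpoints (Protocol 6.1.2).** Long-term MADRS change is to be followed "over time measured in 4 weeks intervals after week 8". EQ-5D-5L is due "at 4 weeks and over time measured in 4 week intervals thereafter (relative to baseline"; IDS-SR and WHODAS-2.0 follow the same pattern. The cost measure has its own timetable: "Cost-effectiveness (modified TiC-P) at 4 and 8 weeks and 3 monthly intervals thereafter (relative to baseline".

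**Assessments (Protocol 6.3).** "During the Induction Phase weekly assessments of effectiveness will be done". In the Continuation Phase the interval is two weeks while dosing is at least weekly. At one dose every two weeks or fewer, "assessments will be done monthly for the first 2 months, followed by every two months thereafter". The text does not say when the first two months begin. The instruments named are "Assessment of baseline MADRS and IDS-SR score" before treatment and "Repeated assessments of MADRS and IDS-SR scores" afterwards.

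**Dosing (Protocol 3.1).** Reduction to two-weekly dosing may be tried from week 9, and "Dosing frequency will be individualized to the lowest frequency to maintain remission/response".

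**Analysis (Protocol 8.1, 8.2).** MADRS differences from baseline are first used over time for the full sample. Linear mixed models are named for the following step, the association with treatment resistance. Section 8.2 plans a comparable approach for IDS-SR, quality of life and functioning.

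**The concern.** The two sections prescribe different measurement schedules for the same endpoints. An 8-week spacing cannot fill a 4-week grid.

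The shortfall is not random. Patients who can hold their response on fewer doses are assessed less often by design, while patients who need at least weekly dosing are always due. If mean change is tabulated at each 4-weekly point from whoever was assessed, the points describe differently selected patients, and movement in the curve may reflect composition, not course of illness. These are secondary endpoints, but long-term effectiveness is part of the primary objective.

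The second issue is collection. EQ-5D-5L, WHODAS-2.0 and TiC-P are defined as changes from baseline, yet Section 6.3 mentions none of them. Across more than 30 listed centres, some may follow Section 6.3 literally, and a baseline questionnaire that was not taken cannot be recovered.

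**Working it through.** The protocol gives no figure to reproduce here, so the check lays the Section 6.3 schedule on the Section 6.1.2 grid.

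**Inputs.** Grid after week 8: weeks 12, 16, ..., 52, that is (52 − 12)/4 + 1 = 11 points. The 52-week horizon is an assumption. Dosing at least weekly: assessed every 2 weeks. Reduced dosing: monthly twice, then two-monthly. A month is taken as 4 weeks unless stated.

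**Formulas.** Let s be the last week on weekly dosing.
- Reading A, two months counted from the reduction: assessments at s + 4, s + 8, s + 16, s + 24, ...
- Reading B, two months counted from the start of Continuation (end of week 4): weeks 8, 12, 20, 28, ..., keeping those after s.
- Before s, the two-weekly schedule applies.

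| Patient | Grid points missed | Grid points covered |
|---|---|---|
| Always at least weekly | none | 11 of 11 |
| A, reduces after week 8 | 20, 28, 36, 44, 52 | 6 of 11 |
| A, reduces after week 12 | 24, 32, 40, 48 | 7 of 11 |
| A, reduces after week 16 | 28, 36, 44, 52 | 7 of 11 |
| A, reduces after week 20 | 32, 40, 48 | 8 of 11 |
| B, reduces after week 8 or 12 | 16, 24, 32, 40, 48 | 6 of 11 |
| B, reduces after week 16 or 20 | 24, 32, 40, 48 | 7 of 11 |

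**Sensitivity.**
- Under A, a reduction after week 10 gives weeks 14, 18, 26, 34, 42 and 50, none of them on the grid.
- With calendar months and a reduction after week 8, assessments fall at weeks 12.3, 16.7, 25.4, 34.1, 42.8 and 51.5. Even with a window of ±2 weeks (assumed), weeks 20, 28, 32, 40 and 48 stay empty.

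**What does not depend on the reading.** Once a patient is on the two-monthly plan, each 8 weeks contains two grid points and one assessment. A patient dosed at least weekly has 8/2 = 4 assessments in the same period. The observation rate therefore differs fourfold between groups that Section 3.1 separates by response.

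**Coverage of the primary endpoint.** Weekly assessment to week 4, then two-weekly assessment during the weekly dosing of weeks 5 to 8, gives MADRS at weeks 4 and 8. MADRS and IDS-SR baselines are scheduled.

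**Instruments.** Section 6.1.2 asks for change from baseline in EQ-5D-5L, WHODAS-2.0 and TiC-P. The text of Section 6.3 contains none of the three, before treatment or after.

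**The case against.** A reader might infer that after week 16 every other 4-weekly point (20, 28, 36, ...) holds only patients still dosed at least weekly. That needs every reduction to come straight after week 8 and the two months to run from it. Section 3.1 individualises the timing. Under reading A, a patient who reduces after week 12 is seen at weeks 20, 28, 36, 44 and 52 and missed at 24, 32, 40 and 48. Under reading B, the thin points are the other alternate set, starting at week 16. The protocol does not say which reading applies, so only systematic under-representation is supported.

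A reader might also want to state the bias in MADRS points. That needs the share of patients on reduced dosing and their score difference from the rest. The protocol gives neither. Staggered reductions would shrink any swing between points, and non-response after 4 weeks is a withdrawal criterion, which may narrow the difference among those who continue.

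It can be said that mixed models are already planned for incomplete repeated data and that details of the full-sample summary belong in an analysis plan. This stands in part. However, Section 8.1 attaches those models to the treatment-resistance step, and they help only if the dependence is captured by the observed data in the model. The mismatch between endpoint and schedule remains a protocol matter.

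On the questionnaires, it would go too far to say that changes in quality of life, functioning and cost cannot be computed. The pre-treatment list in Section 6.3 is framed as eligibility assessment. The section also omits the per-session blood pressure that Section 6.1.2 requires and Section 3.1 confirms is monitored, so it is not exhaustive. Figure 1 is not available and might show more. What stands is that the text of Section 6.3 does not schedule these instruments.

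**Conclusion.** The inconsistency holds. The 4-weekly long-term endpoints cannot be delivered under Section 6.3 for patients on reduced dosing. From about week 16 or 20, depending on when the patient reduces and where the undefined two months start, some grid points systematically under-represent those patients. In the worked cases a patient who reduces has 6 to 8 of 11 exact grid points to week 52, against 11 of 11 for one who does not; reductions off the 4-week rhythm may match none. Because dosing frequency follows response, unadjusted mean changes by visit would compare differently selected patients. The size and direction of that bias cannot be derived from the document. The counts assume a 52-week horizon and 4-week months.

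The primary endpoint at weeks 4 and 8 is not affected. The omission of EQ-5D-5L, WHODAS-2.0 and TiC-P from Section 6.3 is a gap in the written schedule, subject to Figure 1. The point should be corrected, but it does not undermine the main analysis.

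**What to change.** 1. Reconcile Sections 6.1.2 and 6.3 in one assessment schedule that lists every instrument with its baseline and follow-up times. Include EQ-5D-5L, WHODAS-2.0 and TiC-P, with TiC-P kept at weeks 4 and 8 and then 3-monthly. State when the two-month period starts.
2. Replace the 4-weekly long-term MADRS and IDS-SR endpoints with a full-sample trajectory. Use a linear mixed model with continuous time since baseline, all assessments at their actual dates, and patient random effects.
3. Do not report raw means at 4-weekly visits as means of the cohort.

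Two alternatives do not work. A fixed list such as weeks 12, 16, 24, 32 and every 8 weeks after is not common to all: under reading A, a patient who reduces after week 12 misses weeks 24 and 32. Requiring IDS-SR every 4 weeks from everyone conflicts with the statement in Section 6.3 that nothing is measured beyond routine practice.

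**Cost.** Mainly protocol wording; the questionnaires are already endpoints. Long-term results become model-based and rest on data being missing at random given the observed scores, with coarser information for patients on reduced dosing.

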6.4 Withdrawal of individual subjects

Subjects can leave the study at any time for any reason if they wish to do so without any consequences. The investigator can decide to withdraw a subject from the study for urgent medical reasons.

6.4.1 Specific criteria for withdrawal

- Intolerance of esketamine intranasal treatment
- Non-response to the treatment after 4 weeks

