6. METHODS

6.1 Study parameters/endpoints

6.1.1 Main study parameter/endpoint

Primary endpoint is the change (relative to baseline) in clinician-rated MADRS score (Montgomery 1979) at 4 and 8 weeks.

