6.6 Follow-up of subjects withdrawn from treatment

N/A

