8. STATISTICAL ANALYSIS

8.1 Primary study parameter(s)

For the continuous MADRS-scores differences relative to baseline will be used over time. This will initially be done for the full sample.

Subsequently we will investigate the association of the primary outcome with the level of treatment resistance and specific aspects thereof (e.g. ECT-non-responders) with linear mixed models (to accommodate repeated follow-up measurements and unavoidable missing data over time).

For the second aim of the project, we aim to pool this data across different treatment centres in order to increase power and obtain more quantitative information about possible characteristics of responders vs non-responders.

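### Week-4 non-response is listed as a withdrawal criterion and no week-8 assessment is scheduled for those who stop, so the week-8 half of the primary endpoint comes mainly from patients selected on benefit

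*Protocol*

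**What the plan says.** Section 6.1.1: "Primary endpoint is the change (relative to baseline) in clinician-rated MADRS score", measured "at 4 and 8 weeks". Section 8.1 describes the analysis as differences from baseline over time and adds: "This will initially be done for the full sample". Linear mixed models come next, for the association with treatment resistance.

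Section 6.4 is about leaving the study: "The investigator can decide to withdraw a subject from the study for urgent medical reasons". Its subsection 6.4.1 gives two criteria, intolerance and "Non-response to the treatment after 4 weeks". Response is not defined numerically. Section 6.6, headed "Follow-up of subjects withdrawn from treatment", reads N/A.

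Section 6.3 plans weekly effectiveness assessments during induction. After week 4 it schedules MADRS and IDS-SR only within the Continuation Phase, at intervals tied to dosing frequency. The Summary sends treatment responders into that phase. Section 3.1 instead rests the decision on the clinician's "evaluation of symptomatic change and/or improvement in functioning or quality of life".

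Section 6.1.2 lists as a secondary endpoint "Follow-up 3 months after discontinuation of intranasal esketamine treatment", with no instrument or procedure.

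**The concern.** Week 8 falls after the point at which patients are withdrawn for doing poorly. Read together, these sections decide who has a week-8 score partly by the outcome itself. The average change among those still measured will then look better than the average among those who started treatment.

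The primary objective is short- and long-term effectiveness in treated patients. A week-8 figure from continuing patients, reported without that label, would be read as the result for the whole cohort. The same applies to the later scheduled MADRS, IDS-SR, quality-of-life and functioning outcomes. An analysis plan cannot repair this alone, because it cannot supply scores that the protocol does not arrange to collect.

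**Working it through.** **Passages side by side**

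| Question | Where | Answer |
|---|---|---|
| When is the primary endpoint measured? | 6.1.1 | Weeks 4 and 8 |
| In whom is it analysed first? | 8.1 | The full sample |
| Who is withdrawn, and from what? | 6.4, 6.4.1 | Intolerant patients and week-4 non-responders; the parent section concerns the study |
| What follow-up do they have? | 6.6 | N/A (heading refers to treatment) |
| What follow-up do they have? | 6.1.2 | 3 months after discontinuation |
| Who has scheduled MADRS after week 4? | 6.3 | Patients in the Continuation Phase |
| Who enters that phase? | Summary; 3.1 | Responders; those with clinician-judged benefit |

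The 3-month follow-up cannot fill the week-8 gap. Stopping at week 4 plus about 13 weeks is about week 17.

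**Size of the selection effect**

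The protocol made no power calculation and states no mean, SD, response rate or dropout rate, so there is no figure of its own to reproduce. All inputs here are assumptions:
- baseline MADRS mean 32, SD 6, independent of change;
- SD of change 10 at both weeks;
- mean week-8 change -11 to -17;
- mean week-4 change m equal to the week-8 mean or 1 point smaller, so -10 to -17;
- correlation r between week-4 and week-8 change of 0.5 to 0.85;
- patients continue if week-4 improvement is at least a fraction c of baseline, with c = 0.25 or 0.50.

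A patient continues if change + c × baseline ≤ 0. That quantity has SD S = √(10² + c² × 6²). Let a = -(m + 32c)/S. The proportion continuing is Φ(a). The overstatement of the week-8 mean among continuers is r × 10² / S × φ(a)/Φ(a).

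For c = 0.25, S = √(100 + 2.25) = 10.11:
- m = -17: a = 0.890, 81% continue, φ/Φ = 0.330. With r = 0.5: 0.5 × 100/10.11 × 0.330 = 1.6 points.
- m = -10: a = 0.198, 58% continue, φ/Φ = 0.676. With r = 0.85: 0.85 × 100/10.11 × 0.676 = 5.7 points.

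For c = 0.50, S = √(100 + 9) = 10.44:
- m = -17: a = 0.096, 54% continue, φ/Φ = 0.738. With r = 0.5: 3.5 points.
- m = -10: a = -0.575, 28% continue, φ/Φ = 1.196. With r = 0.85: 9.7 points.

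A simulation over a wider assumed grid (baseline 33, SD 6; mean change -8 to -16; SD of change 9 or 12; same correlations) gave 1.5 to 8.3 points at the 25% cut and 3.6 to 12.7 at the 50% cut. The direction was the same in every scenario.

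**What a mixed model could recover**

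In that simulation, regressing week-8 change on baseline and week-4 change recovered the all-patient mean within about 0.2 points. It did so because dropout depended only on observed scores, the relation was linear, and stopped patients kept the trajectory they would have had on treatment. If a fraction p stops and ends d points worse than that trajectory, the model misses p × d. With d = 3 (assumed) and p from 0.19 (1 - 0.81) to 0.72 (1 - 0.28), that is 0.6 to 2.2 points.

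**The case against.** Several counter-arguments have force.

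- **Follow-up exists.** Section 6.1.2 lists a 3-month follow-up after discontinuation, and discontinuation rates with reasons. A reader might infer from 6.6 that patients who stop are never seen again; the documents do not support that. What stands is a contradiction between 6.1.2 and 6.6, and no week-8 value from either.
- **Withdrawal may mean stopping treatment.** Section 6.4 speaks of the study, section 6.6 of treatment, and both 6.4.1 criteria are treatment events. The protocol does not settle this. The ambiguity itself needs correcting, and 6.3 still schedules nothing at week 8 for those who stop.
- **Continuers are not a clean responder group.** Under 3.1 a patient without a MADRS response may continue for better functioning or quality of life. Describing later results as responders only would go too far. The 25% and 50% cuts are illustrations, not protocol rules.
- **Full sample may only contrast with the later analysis by treatment resistance.** That is a fair reading; the phrase need not promise a week-8 score for every starter. Equally, nothing labels the week-8 result as conditional.
- **Mixed models handle missing data.** Weekly MADRS to week 4 makes this partly true. But 8.1 names the model for the association analysis and calls the missing data unavoidable, although the protocol's own withdrawal rule creates part of it.
- **Week 4 stands.** Week-4 MADRS, quality of life and functioning are untouched by the non-response rule. Intolerance before week 4 could still leave some gaps there.

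A reader might also infer that early leavers are dropped from the prediction model. Section 8.3 does not say so, and a separate analysis plan is to be pre-registered for each analysis.

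**Conclusion.** The concern holds in this form: followed as written, the protocol yields week-8 and later scheduled outcomes mainly from patients selected on clinician-judged benefit, and a simple week-8 change from baseline would overstate improvement in the treated cohort. The direction follows from the sections themselves, provided week-4 and week-8 change are positively correlated. The size rests wholly on assumed inputs: about 1.6 to 5.7 points with a 25% retention cut and 3.5 to 9.7 with a 50% cut. These are illustrations, not estimates for this study. A mixed model fitted to all weekly scores could remove most of the bias, but only under an assumption about stopped patients that no scheduled data would test.

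This should be fixed, but it does not undermine the whole study. The cohort is descriptive and uncontrolled, week 4 remains usable, and the remedy is mostly wording and record abstraction.

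**What to change.** 1. State that stopping esketamine is not withdrawal from data collection; only the patient's own wish or the investigator's decision under 6.4 ends data collection.
2. Reconcile the Summary and sections 3.1, 6.1.2, 6.4.1 and 6.6 on who continues, what withdrawal means and what follow-up applies. No clinical stopping rule needs to change for this.
3. Replace N/A in 6.6 with abstraction of routinely recorded MADRS and IDS-SR around week 8 and at 3 months after stopping, for consenting patients.
4. Report week 4 as the full-sample result. Report week 8 and later for all starters where scores exist; otherwise label the results as applying to patients continuing treatment.

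The cost is some extra abstraction, gaps wherever routine care recorded no score, and a less favourable week-8 figure. Abstraction is preferable to new questionnaires for stopped patients. The Summary and 6.3 exclude additional measurements (the Summary excepts the PIT task), and the Summary rests its non-WMO request on this. A delta-adjusted or reference-based sensitivity analysis is an optional choice for the analysis plan, and the point does not depend on it.
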